12.7 Sensitivity analyses

12.7.1 Central laboratory data only

As the primary outcome data may include data from medical records, we will replicate the primary analysis (section 12.6) but only include values that came from central laboratory.

12.7.2 Missing data

The amount of missing data will be reported for each randomised arm, and we will also compare the baseline characteristics of participants who are included in the primary analysis to ensure that any attrition has not produced any imbalance in the groups in important covariates. We will explore the extent and pattern of missing data and, if appropriate, will undertake multiple imputation to assess the impact of missing data on treatment effect estimates.

Multiple Imputation by Chained Equation (MICE) will be used as the method for imputation (10)(11). The imputation model that will be used to impute Hba1c at baseline, 6 months and 12 months. We will present results from the following models:

Baseline imputed only- the imputation model will include HbA1c at baseline and 6 months, age, sex, ethnicity, IMD decile and treatment arm. Thirty multiply imputed data sets will be used. Missing 12-month HbA1c values will be imputed but removed again before analysis (12)

Baseline and 12 months- the same model described above will be used and the imputed 12-month HbA1c values will remain.

Treatment effects and their 95% CIs will be presented in a forest plot alongside those produced using the primary analysis methods and other sensitivity analyses (Ref: Table 7).

12.7.3 CACE analysis

Complier Average Causal Effect (CACE) analyses will be performed for the primary outcome to assess the impact of compliance on treatment estimates. This will be conducted at the participant level, considering compliance as a dichotomous variable (complied or not). Compliance to the intervention is difficult to pre-define as there are several components to the intervention (one-to-one sessions, workbook, app use) and is intended to be flexible. An intervention participant will be defined as noncompliant if they do not attend any coaching sessions. An instrumental variable approach will be used, with random group allocation as the instrumental variable (13).

12.8 Subgroup analyses

Subgroup analyses will be performed to explore the potential effect of the following subgroups:

- Participants with good and those with suboptimal diabetes control at baseline as defined as High control (HbA1c values <= 58 mmol/mol) and Low control (HbA1c values >58 mmol/mol)
- Ethnicity (White, Asian or Asian British, Black, Black British, Caribbean or African, Mixed or multiple ethnic groups or Other Ethnic background)
- Insulin use status (Prescribed insulin Yes or No)
- Urdu speakers (Yes or No)

DIAMONDS Statistical Analysis Plan version 1

As we are unable to predetermine the numbers in each subgroup, the completion of each subgroup analysis will be subject to there being sufficient numbers in the group.

The primary analysis model will be refitted with an interaction term between the randomisation group and the specified subgroup variable. Treatment effect for these subgroups will be reported as adjusted mean differences with their associated 95% CI and p-values (Ref: Table 8). As recommended by the literature, the subgroup analysis will be restricted to the primary analysis

and subgroups will be defined by baseline data i.e. data that is not dependent on the intervention(14). Subgroup analysis will be performed regardless of the results of the primary analysis.

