8.2 External datasets

8.2.1 Intervention delivery

Data on the delivery of the intervention will be collected via Qualtrics and the Change One Thing app:

- Session duration;
- Number of sessions delivered;
- Mode of delivery (remote, phone, in person): frequencies/percentages;
- List of content areas with number of participants who discussed each content area;
- Duration a participant stayed with the same action plan/content area;
- Number of content areas covered during total intervention period and workbook and/or Change One Thing app.

9 Sample Size

Original sample size calculation

The sample size calculation was based on detecting a clinically meaningful difference of 5.5 mmol/mol (0.5%) in HbA1c at 12 months. This difference was selected based on data from trials of diabetes self-management in the general diabetes population and NICE guideline on type 2 diabetes management. Based on the variation observed in HbA1c in a Clinical Practice Research Datalink (CPRD) population study, we assumed a standard deviation of 15.3 mmol/mol. Based on attrition rates in previous severe mental illness trials, we expect approximately 20% attrition. In the intervention arm, a DIAMONDS Coach will deliver the intervention to multiple participants, and therefore the outcomes of participants with the same coach may be correlated. Although only a small clustering effect is expected, this provides a more conservative sample size estimate. The sample size was therefore adjusted for clustering in the intervention arm.

For approximately 90% power, at the 5% significance level, assuming an average cluster size of 10-12 participants per DIAMONDS coach with an intraclass correlation (ICC) of 0.02 in the intervention

DIAMONDS Statistical Analysis Plan version 1 Page | 10 arm, and adjusting for 20% attrition, we estimate we will need to randomise 450 participants, with 225 per treatment group.

Revised sample size calculation

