In February 2024 following discussion with the TSC, an amendment was made to the original sample size calculation described above due to slower than anticipated recruitment. We amended the sample size by including an adjustment for the correlation between baseline and 12-month HbA1c (0.3) to reflect the repeated measures analysis model planned for the primary analysis. This led to a minimum sample size of 380 participants needed; keeping all other assumptions the same would achieve 88% power. However, we will continue recruiting beyond this minimum target until the end of the agreed recruitment window.

10 Randomisation and blinding

As stated in the protocol:

Consenting participants will be randomised on a 1:1 allocation ratio to either the DIAMONDS intervention or the usual care group using computer generated permuted blocks of random sizes. Randomisation will be carried out by York Trials Unit (YTU) independently of the R&D team using a secure, online randomisation service to ensure allocation concealment.

The DIAMONDS Programme Manager and Trial Coordinators will be unblinded to allocation in order to facilitate contact between randomised participants and their designated DIAMONDS Coach, if required. Following randomisation, the participating site will contact DIAMONDS Coaches to advise them to approach participants randomised to the intervention group to arrange the first intervention session.

Statisticians will not remain blind during the study but will not see any unblinded primary outcome data until a version 1 of the statistical analysis plan has been signed off.

11 Analysis of internal pilot trial/phase

As stated in the protocol:

Recruitment rate and the 95% confidence interval will be estimated from the pilot data collected. A CONSORT diagram will produced with the following outcomes: number of eligible participants; proportion of eligible participants approached for consent; proportion of eligible participants not approached and reasons why; proportion of participants approached who provide consent; proportion of participants approached who do not provide consent; proportion of participants providing consent who are randomised; proportion of participants randomised who do not receive the randomly allocated treatment; proportion of participants dropping out between randomisation and follow-up.

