12.2 Analysis principles and populations

Analysis of primary and secondary outcomes will be intention-to-treat (ITT) (unless otherwise stated) and tests will be two sided at 5% significance level.

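### Section 12.8 tests effect modification by baseline HbA1c only through a split at 58 mmol/mol; a continuous interaction should be added alongside it

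*SAP*

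**What the plan says.** Section 12.8 lists four subgroup variables: diabetes control, ethnicity, insulin use and Urdu speaking. Diabetes control is defined by a cut in baseline HbA1c: "Participants with good and those with suboptimal diabetes control at baseline as defined as High control (HbA1c values <= 58 mmol/mol"), with low control above 58. The primary model is refitted with an interaction between randomised group and the subgroup variable. For all four variables, "the completion of each subgroup analysis will be subject to there being sufficient numbers in the group"; no minimum number is given.

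The primary model in section 12.6 adjusts for baseline HbA1c but contains no treatment-by-baseline interaction, and none is planned elsewhere. Appendix Table 1 lists severe mental illness, age 18 or over, type 2 diabetes of at least three months and several exclusions, but no HbA1c criterion. Section 9 bases the sample size on "detecting a clinically meaningful difference of 5.5 mmol/mol (0.5%) in HbA1c at 12 months".

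**The concern.** With no HbA1c floor listed, the trial can enrol people across a wide range of glycaemic control, and section 12.8 itself expects some at or below 58. If the average effect turns out small, readers will ask whether the intervention does little for anyone or does more where HbA1c is raised. Only one planned analysis addresses this. Its effect-modification term assigns one treatment effect to everyone from 59 upwards and another to everyone at 58 or below.

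The information for a finer answer is already in the model. If the effect varies gradually with baseline HbA1c, the cut gives up power in a comparison that has little to spare. What is at stake is the interpretation of the primary result, not the result itself.

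**Working it through.** **Inputs from the SAP.** Section 9: "we assumed a standard deviation of 15.3 mmol/mol"; "we expect approximately 20% attrition"; "assuming an average cluster size of 10-12 participants per DIAMONDS coach", with ICC 0.02 in the intervention arm; revised minimum of 380 with a baseline to 12-month correlation of 0.3. Section 10: "randomised on a 1:1 allocation ratio". Section 12.2: "tests will be two sided at 5% significance level".

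**Inputs assumed.** Normal baseline HbA1c with SD 15.3 and mean 53, 58, 63 or 68. The SAP gives neither a baseline mean nor an expected share above 58.

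**Step 1: the plan's own figures.** Normal approximation, design effect 1 + (m − 1) × 0.02 in the intervention arm only.
- 450 randomised leaves 450 × 0.8 / 2 = 180 per arm. For m = 10, SE = 15.3 × √((1.18 + 1)/180) = 1.684 and power = Φ(5.5/1.684 − 1.96) = 90.4%. For m = 12 it is 89.9%. The stated figure is about 90%.
- 380 randomised leaves 152 per arm, 304 in all. With variance multiplied by 1 − 0.3² = 0.91, power is 88.2% (m = 10) to 87.7% (m = 12). The stated figure is 88%.

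Both reproduce. The SAP gives no power for any subgroup analysis.

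**Step 2: information kept by the split if effect modification is linear.** For a normal modifier this is φ(z)² / (q(1 − q)), where z = (58 − mean)/15.3 and q is the share at or below 58.

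| Assumed mean | q | Information kept | Loss | Smaller side of 304 |
|---|---|---|---|---|
| 53 | 0.63 | 0.61 | 39% | 113 |
| 58 | 0.50 | 0.64 | 36% | 152 |
| 63 | 0.37 | 0.61 | 39% | 113 |
| 68 | 0.26 | 0.54 | 46% | 78 |

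The best case is a cut at the median, which keeps 2/π = 0.64; the same interaction power then needs 1/0.637 = 1.57 times as many participants. Over a wider set of assumptions (means 50-70; normal, lognormal, or gamma shifted to a minimum of 35), the loss ran from 35% to 61%.

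**Step 3: what this means for power under linearity.** With 304 analysed, one time point and no coach clustering, the SE of the change in effect per baseline SD is 2 × 15.3 × √0.91 / √304 = 1.67. With the cut at the median:

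| Change in effect per baseline SD (mmol/mol) | Continuous | Split |
|---|---|---|
| 2.75 | 38% | 26% |
| 4.0 | 67% | 48% |
| 5.5 | 91% | 75% |

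**Step 4: other shapes.** Simulation, again with 304 analysed, one time point and no clustering.
- *Exact step at 58* (no effect at or below; above it, 5.5 divided by the share above, so that the average is 5.5). Power for split against continuous was 98% v 89% at mean 53, 90% v 73% at 58, 71% v 51% at 63, and 47% v 29% at 68. The split wins.
- *Benefit growing gradually above 48 or above 58.* Over the assumed means, power was 57-99% continuous against 35-98% split. The continuous term wins at every mean.

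**The case against.** The strongest objection is that the shape of any effect modification is unknown. If the intervention helps only people above 58, and helps them equally, the split is the right test and replacing it would lose power. Step 4 confirms this. The objection defeats any proposal to drop the split or reduce it to a display. It does not defeat adding a continuous term, which does better when the benefit grows with baseline HbA1c.

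Four stronger readings are tempting, and the SAP does not support them.
- A reader might infer that the split discards over a third of the information as a matter of fact. That holds only under approximate linearity; under a step at 58 the split loses nothing.
- A reader might infer that people at or below 58 have no room to improve. The SAP speaks only of good and suboptimal control and says nothing about who can respond.
- A reader might infer that the sufficient-numbers condition will remove this analysis. Under the assumptions above, the smaller side holds about 78-152 of 304. The condition covers all four subgroup variables, and small groups are more plausible for ethnicity or Urdu speaking.
- A reader might infer that averaging over all enrolled participants is itself a defect. Objective 2 asks for the effect in those randomised, and eligibility belongs to the protocol, which is not shown. The absence of a floor is established only for the criteria listed in the SAP.

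It is also fair that the refitted model keeps baseline HbA1c as a continuous main effect, so only the interaction is binary. Nor is the continuous test powerful when modification is modest: 38% in the weakest case in Step 3.

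**Conclusion.** The point stands as a worthwhile improvement to an exploratory analysis. The split at 58 is the only planned look at effect by baseline HbA1c, although the continuous measure is already in the model.

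If effect modification is about linear, the split loses about 36-46% of the interaction information. This rests on normal baseline HbA1c with SD 15.3 (section 9) and an assumed mean of 53-68. Among the shapes examined, the split was better only for a true step at 58. Since the shape is unknown, the plan is best served by both analyses. The primary estimate, the sample size of 380 and its 88% power are untouched.

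**What to change.** In section 12.8:
- Add a treatment by continuous baseline HbA1c interaction to the primary model, specified at 12 months. The model holds both follow-up times, and the present text does not say whether the subgroup term refers to 12 months or is common to both.
- Check linearity with a prespecified spline.
- Report the interaction estimate with its 95% CI, and the 12-month treatment difference with 95% CI at a few prespecified baseline values.
- Keep the prespecified 58 split interaction alongside it.
- State that the continuous analysis does not depend on the sufficient-numbers condition, since it has no subgroup cell to fill.

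At the same time, correct the appendix Table 8 shell, which labels both the high and the low control rows as at or below 58 and so contradicts section 12.8.

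Record the change in the section 13 log, stating whether outcome data by arm had been seen by then; section 10 protects the statisticians from unblinded primary outcome data only until version 1 is signed off.

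The cost is SAP wording and one further model using data already collected. The downsides are one more exploratory test and a linearity assumption, which the spline checks.

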12.6 Primary analysis

The primary outcome (HbA1c at 12-month post-randomisation) will be analysed using a partiallynested mixed effects regression model, with HbA1c scores at 6- and 12-months follow-up as the dependent variable, adjusting for baseline HbA1c scores and outcome source (central lab or medical records), randomised treatment group, time and a treatment group-by-time interaction will be included as fixed effects and participant and DIAMONDS coach as a random effect nested within treatment arm (9). Different covariance patterns for the repeated measurements will be explored and the most appropriate pattern will be used for the final model. Diagnostics including Akaike's information criterion will be compared for each model (smaller values are preferred). The model assumptions (normality of residuals, homoskedasticity and multicollinearity) will be evaluated using residual plots and calculating variance inflation factors (VIFs).

The estimated treatment group difference at 12 months will be reported as the primary endpoint with the associated 95% confidence interval and p-value (Ref: Table 7). Analysis of the primary outcome will be checked by a second statistician. The analysis model does not match exactly the method used in the sample size calculation which simply compares one follow up point (12 months) with an adjustment for baseline correlation. This is a more conservative approach so we should still have adequate power for the primary analysis.

HbA1c is being collected from different sources:

Central laboratory- participant must consent to bloods being taken at their visit. The sample is then sent to a central laboratory in Manchester. Blood results are returned to YTU and recorded on a Bloods CRF by YTU staff.

Medical records- if lab results are unavailable (e.g. participant refuses to have blood samples taken), the investigator may use medical records to look up a recent blood test result and corresponding date which will be recorded on that CRF (baseline, Month 6 or Month 12).

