Number of cigarettes smoked			
on an average day			
n (% of smokers)			
Mean (SD)			
Not reported			
EQ5D-5L score			
n (%)			
Mean (SD)			
Median (IQR)			
Min, Max			

Table 4: Participant Withdrawals

Site	Allocation	Full Withdrawal	Withdrawal from intervention	Withdrawal from follow-up	Died

Table 5: Data completeness by time-points

Outcome	Ba	Baseline 6 Weeks 6 months		6 Weeks		nonths
Outcome measure	Control	Intervention	Control	Intervention	Control	Intervention
	N (%) N (%)	N (%)	N (%)	N (%)	N (%)	

Table 6: Summary of intervention delivery

Intervention delivery	Total
Session duration	
Ν	
Mean (SD)	
Median (IQR)	
Number of sessions per	
participant	
Ν	
Mean (SD)	
Median (IQR)	
Mode of delivery, N (%)	
Remote	
Phone	
In person	
Content areas covered,	
N (%)	
Duration of action plans	
Ν	
Mean (SD)	
Median (IQR)	
Content areas covered	
during total intervention	
Ν	
Mean (SD)	
Median (IQR)	

Table 7: Primary analysis including sensitivity analyses

	Mean (SD)	Adjusted	
	Intervention	Control	Mean Difference (95% Cl, p- value)
HbA1c			
Number of participants			
12 Months			
Sensitivity analysis			
Central laboratory data only			
Missing data			
Baseline only			
Baseline and 12 months			
CACE analysis			

Table 8: Subgroup analysis

		n (%)	Adjusted Mean Difference (95% CI, p-value)
Diabetes control	High (<=58mmol/mol)		
	Low (<=58mmol/mol)		
Prescribed insulin	Yes		
	No		
Speaks Urdu	Yes		
	No		
Ethnicity	Group 1		
	 Group #		

Table 9: Secondary analysis

	Intervention	Control	Difference (95% Cl, p- value)	
Hba1c	Mean (SD)	Mean (SD)		
Number of participants				
6 Months				
ВМІ				
n				
6 Months				

			Adjusted
	Intervention	Control	Mean Difference (95% Cl, p- value)
n			
12 Months			
PHQ-9 score			
n			
6 Months			
12 Months			
BPRS score			
n			
6 Months			
n			
12 Months			
PAID-5 score			
n			
6 Months			
n			
12 Months			
	n (%)	n (%)	Odds ratio (95% CI)
Smoked within last 7 days (Y/N)			
n			
6 Months			
n			
12 Months			

Table 10: Summary of secondary outcomes

	Intervention	Control	Total
Waist circumference			
(cm)			
Ν			
Mean (SD)			
Median (IQR)			
Not reported			
Systolic Blood pressure			
N			
Mean (SD)			
Median (IQR)			
Not reported			
Diastolic Blood pressure			
Ν			
Mean (SD)			

	1	
Median (IQR)		
Not reported		
Total cholesterol		
Ν		
Mean (SD)		
Median (IQR)		
Not reported		
LDL cholesterol		
Ν		
Mean (SD)		
Median (IQR)		
Not reported		
HDL cholesterol		
Ν		
Mean (SD)		
Median (IQR)		
Not reported		
Haemoglobin		
N		
Mean (SD)		

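### SAP 12.8 and Table 8 report a p-value within each subgroup level but no interaction result, and the 12-month subgroup contrast rests on an unstated assumption of equal effect modification at both visits

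*SAP*

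**What the plan says.** The primary model in SAP section 12.6 is a repeated-measures model "with HbA1c scores at 6- and 12-months follow-up as the dependent variable". Its terms include baseline HbA1c, outcome source and the following: "randomised treatment group, time and a treatment group-by-time interaction will be included as fixed effects". The treatment difference at 12 months is the primary endpoint.

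Section 12.8 lists four subgroup factors: diabetes control at baseline, ethnicity, insulin use and speaking Urdu. For each, "The primary analysis model will be refitted with an interaction term between the randomisation group and the specified subgroup variable". On reporting it says: "Treatment effect for these subgroups will be reported as adjusted mean differences with their associated 95% CI and p-values". It adds that "the subgroup analysis will be restricted to the primary analysis".

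Table 8 in the appendices has one result column, "Adjusted Mean Difference (95% CI, p-value", with one row per subgroup level. It has no row or column for an interaction estimate or test, and no time label, although Tables 7 and 9 label their time points. Its second diabetes-control row reads "Low (<=58mmol/mol", the same range as the first row, whereas section 12.8 defines that stratum as above 58 mmol/mol.

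**The concern.** Two things need settling.

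**Reporting.** A p-value within a subgroup level tests whether the effect in that level is zero. Whether the effect differs between levels is a separate question, answered by the interaction term. The plan fits that term but does not commit to reporting it. With the groups listed in section 12.8, Table 8 would hold 2 + 2 + 2 + 5 = 11 within-level p-values and no interaction p-value. This layout invites the inference that a treatment works in one group and not in another because only one p-value is below 0.05. Section 12.8 says the subgroup numbers cannot be known in advance, so uneven splits are likely for some factors, and they make discordant p-values more common.

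**Time point.** The model has two follow-up visits, and the only addition named is a group-by-subgroup term. The difference in effect between subgroups is then constrained to be the same at 6 and 12 months. Under section 12.5 coaching sessions are offered over six months, so equal modification at the end of delivery and six months later is an assumption that ought to be stated.

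**Working it through.** **Inputs from the SAP (sections 9 and 12.2).** Difference 5.5 mmol/mol; SD 15.3; correlation between baseline and 12 months 0.3; ICC 0.02 with 10 to 12 participants per coach, intervention arm only; attrition 20%; 380 randomised, 1:1; two-sided 5%.

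**Step 1: reproduce the plan's power.** Number analysed: 380 × 0.8 = 304, or 152 per arm. Adjusted variance: 15.3² × (1 − 0.3²) = 234.09 × 0.91 = 213.02. Design effect with 11 per coach: 1 + 10 × 0.02 = 1.20. Standard error of the treatment difference: √[213.02 × (1 + 1.20)/152] = 1.756. Power: Φ(5.5/1.756 − 1.96) = Φ(1.17) = 0.88. This matches the stated 88%. The sample size is not in dispute.

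**Step 2: discordant subgroup p-values when there is no effect modification.** For a subgroup holding a fraction f of participants, SE = 1.756/√f and power = Φ(5.5/SE − 1.96). With powers p1 and p2, and the two estimates treated as independent, the chance that exactly one is significant is p1(1 − p2) + p2(1 − p1). The splits are assumptions; the SAP gives none.

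| Split | Power, smaller group | Power, larger group | Exactly one p<0.05 |
|---|---|---|---|
| 50:50 | 0.60 | 0.60 | 48% |
| 30:70 | 0.40 | 0.75 | 55% |
| 20:80 | 0.29 | 0.80 | 63% |
| 10:90 | 0.17 | 0.84 | 73% |

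Without the coach design effect the last column is 46%, 54%, 63% and 74%. With 360 analysed (450 × 0.8) and the design effect kept, it is 44%, 52%, 62% and 75%.

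**Step 3: power of the proper test.** The interaction SE at a single time point is 1.756/√[f(1 − f)]. At 50:50 this is 3.51, and power for a 5.5 mmol/mol difference between subgroups is Φ(5.5/3.51 − 1.96) = 0.35. At 10:90 it is about 0.16.

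**Step 4: what the two-way model estimates.** Code time as 0 at 6 months and 1 at 12 months. In the model as written, the 12-month effect is arm + arm×time in the reference subgroup, and arm + arm×time + arm×subgroup in the other. The arm×subgroup coefficient is therefore the assumed modification at both visits. If modification really differs, it estimates a weighted mean of the two. Assume for illustration (none of this is in the SAP) two equal subgroups, 10% missing at 6 months, 20% missing at 12 months and a 6-to-12-month residual correlation of 0.3 to 0.7. The weights are then roughly 54:46.

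| True modification, 6 / 12 months | True 12-month effects | Two-way model, 12 months | Interaction reported |
|---|---|---|---|
| 5.5 / 5.5 | −3.0, −8.5 | −3.0, −8.5 | 5.5 |
| 0 / 5.5 | −3.0, −8.5 | about −4.5, −7.0 | about 2.5 |
| 5.5 / 0 | −3.0, −3.0 | about −1.5, −4.5 | about 3.0 |

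Adding subgroup×time and arm×subgroup×time recovers the true 12-month values in every row.

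**Step 5: the price in precision.** Under the same assumptions, without coach clustering and with 304 participants before that missingness, the interaction SE at correlations 0.3, 0.5 and 0.7 is 2.86, 3.03 and 3.18 for the two-way model. With the three-way term it is 3.71, 3.66 and 3.57. The ratios are 1.30, 1.21 and 1.12. Starting from 380 randomised, all SEs shrink by √(304/380) = 0.894, to about 2.6–2.8 against 3.2–3.3, with the same ratios.

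**The case against.** The defence has real substance.

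- A reader might infer that Table 8 cannot give a 12-month subgroup effect at all. The SAP does not support that. The refitted model keeps the group-by-time term, so a 12-month contrast can be formed for each subgroup. Restricting subgroup work to the primary analysis also points to 12 months. If modification is equal at both visits, that contrast is exact and more precise than the three-way version.
- A reader might also infer that no test of effect modification is planned. In fact the interaction term is fitted. Only the commitment to report it is missing.
- The bias in step 4 is conditional. The SAP gives no figure for how modification might change between visits. With power of about 35% for the interaction even at 50:50, a more parsimonious model is a defensible choice.
- The discordance figures do harm only if someone reads modification into them, and the SAP attaches no decision rule to subgroup p-values. Also, 304 analysed is a floor, because 380 is a minimum target, and each subgroup analysis depends on sufficient numbers.
- The repeated range in Table 8 is clerical, since section 12.8 defines the strata correctly.

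All of this stands. It limits the point without removing it: Table 8 as laid out shows the p-values that do not answer the subgroup question and omits the one that does. Neither the contrast nor the constant-modification assumption is written down.

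**Conclusion.** The point holds, at minor to moderate weight. As written, section 12.8 and Table 8 report within-level tests and leave out the interaction estimate and its test. Under a uniform effect of 5.5 mmol/mol, discordant p-values would arise in about 48% to 63% of trials for splits from 50:50 to 20:80. That rests on the SAP's SD, correlation, ICC and attrition, 11 participants per coach, 304 analysed and assumed splits. It changes little without clustering or with 360 analysed. Separately, the 12-month subgroup contrast is valid only if modification is the same at 6 and 12 months. The SAP does not state this, and the size of any error depends on modification patterns for which it gives no figures. It would be too strong to say that the subgroup effects will be wrong. The analyses are exploratory, and the primary estimate, interval and p-value are unaffected.

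**What to change.** 1. In section 12.8, name the treatment contrast at 12 months as the quantity reported for each subgroup.
2. In Table 8, give for each factor the 12-month subgroup differences with 95% CI, plus one interaction estimate with 95% CI and one interaction p-value. Use a joint test for ethnicity, which has more than two levels. Let these replace the per-level p-values, and label the table as 12 months.
3. Either add subgroup-by-time and group-by-subgroup-by-time terms, or keep the two-way term and state that modification is assumed constant over the two visits.
4. Correct the second diabetes-control label in Table 8 to >58 mmol/mol.

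An interaction with continuous baseline HbA1c would be a reasonable extra for the diabetes-control factor, but it is optional.

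The cost is a few sentences and one table shell. The three-way option widens the interaction interval by about 12% to 30% under the illustrative assumptions above (SE about 3.6–3.7 against 2.9–3.2 on the 304-participant basis). Stating the assumption instead costs no precision, but the result then depends on it.
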